Table 1-1 IXADES Treatment Protocol

| 28-Day Cycle (a 4-week cycle) | | | | | | | | |
|-------------------------------|--------|----------|--------|-----------|--------|------------|--------|------------|
| | Week 1 | | Week 2 | | Week 3 | | Week 4 | |
| | Day 1 | Days 2-7 | Day 8 | Days 9-14 | Day 15 | Days 16-21 | Day 22 | Days 23-28 |
| Ixazomib (NINLARO) 3 mg | ✓ | | ✓ | | ✓ | | | |
| Dexamethasone 20 mg | ✓ | | ✓ | | ✓ | | | |

Figure 1. Study Overview Diagram

Ixazomib for Desensitization (IXADES) in Kidney Transplantation

SCHEDULE OF EVENTS
Table 2-1 (a)-Schedule of events (first six cycles)

| Procedures Performed | Screening (<=/ 30 days) | Cycle 1 (< /= 3 months after screening) | | | Cycle 2 | | Cycle 3 | | | Cycle 4 | | | Cycle 5 | | | Cycle 6 | | |
|------------------------------------|-------------------------|---|---|----|---------|----|---------|----|----|---------|----|----|---------|-----|-----|---------|-----|-----|
| | | 1 | 8 | 15 | 29 | 36 | 43 | 57 | 64 | 71 | 85 | 92 | 99 | 113 | 120 | 127 | 141 | 148 |
| Treatment Days (+6, -3) | | | | | | | | | | | | | | | | | | |
| Ixazomib and Dexamethasone | | X | X | X | X | X | X | X | X | X | X | X | X | X | X | X | X | X |
| Medical History | X | X | | | | | | | | | X | | | X | | | X | |
| Physical Exam | X | X* | | | | | | | | | X | | | | | | | |
| Vital Signs (T, P, R, BP) | X | X | | | X | | | X | | | X | | | X | | | X | |
| AE Assessment | | X | | | X | | | X | | | X | | | X | | | X | |
| Electrocardiogram (ECG) | X | | | | | | | | | | | | | | | | | |
| Echocardiogram | X | | | | | | | | | | | | | | | | | |
| Medication History | X | X | | | X | | | X | | | X | | | X | | | X | |
| Drug Accountability | | | | | X | | | X | | | X | | | X | | | X | |
| Pregnancy Test (where appropriate) | X | | | | | | | | | | | | | | | | | |
| CBC | X | X | | | X | | | X | | | X | | | X | | | X | |
| LFTs | X | X | | X | X | | X | X | X | | X | | | X | | | X | |
| cPRA | | X | | | | | | | | | X | | | | | | | |
| BAFF/APRIL | | X | | | | | | | | | X | | | | | | | |
| DSA Antibodies | | X | | | | | | | | | X | | | | | | | |
| Bone Marrow Aspiration | | X ¹ | | | | | | | | | | | | | | | | |

*Physical examination to be completed at visit 1, if not completed during screening visit.

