1 Bone Marrow Aspiration must be done before drug administration and at one of the following endpoints: one month (+6, -3 days) after the end of the 12 month study, cPRA decline > 20%, time of transplant, or time of subject withdrawal from the study.

Table 2-1 (b)-Schedule of events (last six cycles)

| Procedures Performed | Cycle 7 | | | Cycle 8 | | | Cycle 9 | | | Cycle 10 | | | Cycle 11 | | | Cycle 12 | | | Final visit 1M after last dose | ETV or Unscheduled Visit |
|------------------------------------|---------|-----|-----|---------|-----|-----|---------|-----|-----|----------|-----|-----|----------|-----|-----|----------|-----|----------------|--------------------------------|--------------------------|
| Treatment Days | 169 | 176 | 183 | 197 | 204 | 211 | 225 | 232 | 239 | 253 | 260 | 267 | 281 | 288 | 295 | 309 | 316 | 323 | 373 | |
| Ixazomib and dexamethasone | X | X | X | X | X | X | X | X | X | X | X | X | X | X | X | X | X | X | | |
| Medical History | X | | | | | | | | | X | | | | | | | | | X | |
| Physical Exam | X | | | | | | | | | X | | | | | | | | | X | |
| Vital Signs (T, P, R, BP) | X | | | X | | | X | | | X | | | X | | | X | | X | X | |
| AE Assessment | X | | | X | | | X | | | X | | | X | | | X | | X | X | |
| Electrocardiogram (ECG) | X | | | | | | | | | | | | | | | | | | X | |
| Echocardiogram | X | | | | | | | | | | | | | | | | | | X | |
| Medication History | X | | | X | | | X | | | X | | | X | | | X | | X | X | |
| Drug Accountability | | | | X | | | X | | | X | | | X | | | X | | X | X | |
| Pregnancy Test (where appropriate) | | | | | | | | | | | | | | | | | | | | |
| CBC | X | | | X | | | X | | | X | | | X | | | X | | | X | |
| LFTs | X | | | X | | | X | | | X | | | X | | | X | | | X | |
| cPRA | X | | | | | | | | | X | | | | | | | | | X | |
| BAFF/APRIL | X | | | | | | | | | X | | | | | | | | | X | |
| DSA Antibodies | X | | | | | | | | | X | | | | | | | | | X | |
| Bone Marrow Aspiration | | | | | | | | | | | | | | | | | | X ¹ | X ¹ | |

TABLE OF CONTENTS

| | |
|---|----|
| PROTOCOL SUMMARY..... | 3 |
| STUDY OVERVIEW DIAGRAM (optional)..... | 6 |
| SCHEDULE OF EVENTS..... | 7 |
| LIST OF TABLES AND FIGURES (OPTIONAL)..... | 11 |
| LIST OF ABBREVIATIONS AND GLOSSARY OF TERMS..... | 12 |
| 1. BACKGROUND AND STUDY RATIONALE | 13 |
| 1.1 Scientific Background | 13 |
| 1.1.1 Disease Under Treatment..... | 13 |
| 1.1.2 Ixazomib (MLN9708) | 14 |
| 1.2 Preclinical Experience | 14 |

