Ixazomib is neither a time-dependent inhibitor nor a reversible inhibitor of CYPs 1A2, 2B6, 2C8, 2C9, 2C19, 2D6, or 3A4/5. Ixazomib did not induce CYPs 1A2, 2B6, and 3A4/5 activity or corresponding immunoreactive protein levels. Thus, the potential for ixazomib to produce DDIs via CYP isozyme induction or inhibition is low.

Ixazomib is not a substrate of BCRP, MRP2 and OATPs. Ixazomib is not an inhibitor of Pgp-, BCRP, MRP2, OATP1B1, OATP1B3, OAT1, OAT3, OCT2, MATE1 and MATE2K. Ixazomib- is unlikely to cause or be susceptible to clinical DDIs with substrates or inhibitors of clinically relevant drug transporters.

The geometric mean terminal halflife- ($t_{1/2}$) of ixazomib is 9.5 days based on population PK analysis. For both IV and oral dosing, there is an approximately average 3fold accumulation (based on AUC) following the Day 11 dose for the -twiceweekly- schedule and a 2fold accumulation (based on AUC) following the Day 15 dose for the -onceweekly- schedule.

Mean plasma clearance (CL) of ixazomib is 1.86 L/hr based on the results of a population PK analysis. Taken together with the blood-to-plasma AUC ratio of approximately 10, it can be inferred that ixazomib is a low clearance drug. Using the absolute oral bioavailability (F) estimate of 58% (also from a population PK model), this translates to an apparent oral plasma clearance (CL/F) of 3.21 L/hr. The geometric mean renal clearance for ixazomib is 0.119 L/hr, which is 3.7% of CL/F and 6.4% of CL estimated in a population PK analysis. Therefore, renal clearance does not meaningfully contribute to ixazomib clearance in humans. Approximately 62% of the administered radioactivity in the ADME study (Study C16016) was recovered in the urine and 22% of the total radioactivity was recovered in the feces after oral administration. Only 3.2% of the administered ixazomib dose was recovered in the urine as unchanged ixazomib up to 168 hours after oral dosing, suggesting that most of the total radioactivity in urine was attributable to metabolites.

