In the 4 ongoing studies (C16003, C16004, C16007, and C16009) investigating single-agent oral ixazomib in patients with differing malignancies (multiple myeloma, AL amyloidosis, nonhematologic cancers, and lymphoma), a total of 201 patients have been treated as of 27 March 2013. These patients have been treated with different doses of ixazomib as they are all phase 1 trials. An overview of the most frequent (at least 10%) AEs occurring in the pooled safety population from single-agent oral ixazomib Studies (C16003, C16004, C16007, and C16009) is shown in Table 3-2.

Table 3-2 Most Common (At Least 10% of Total) Treatment-Emergent Adverse Events in Oral Single-Agent Studies

| Primary System Organ Class Preferred Term | Oral Single Agent | |
|--|--------------------------|--------------------------|
| | Total | n = 201 n (%) |
| Subjects with at Least One Adverse Event | 197 (98) | |
| Gastrointestinal disorders | 160 (80) | |
| Nausea | 106 (53) | |
| Diarrhoea | 88 (44) | |
| Vomiting | 77 (38) | |
| Constipation | 46 (23) | |
| Abdominal pain | 33 (16) | |
| General disorders and administration site conditions | 151 (75) | |
| Fatigue | 103 (51) | |
| Pyrexia | 51 (25) | |
| Oedema peripheral | 27 (13) | |
| Asthenia | 31 (15) | |
| Nervous system disorders | 92 (46) | |
| Headache | 29 (14) | |
| Dizziness | 26 (13) | |
| Neuropathy peripheral | 21 (10) | |
| Metabolism and nutrition disorders | 107 (53) | |
| Decreased appetite | 64 (32) | |
| Dehydration | 37 (18) | |
| Blood and lymphatic system disorders | 98 (49) | |
| Thrombocytopenia | 68 (34) | |

Table 3-2 Most Common (At Least 10% of Total) Treatment-Emergent Adverse Events in Oral Single-Agent Studies

| Primary System Organ Class Preferred Term | Oral Single Agent | |
|---|-------------------|---------|
| | Total | n = 201 |
| | n (%) | |
| Anaemia | 42 (21) | |
| Neutropenia | 29 (14) | |
| Lymphopenia | 20 (10) | |
| Skin and subcutaneous tissue disorders | 90 (45) | |
| Rash macular ^a | 23 (11) | |
| Musculoskeletal and connective tissue disorders | 93 (46) | |
| Back pain | 24 (12) | |
| Arthralgia | 28 (14) | |
| Respiratory, thoracic and mediastinal disorders | 78 (39) | |
| Cough | 28 (14) | |
| Dyspnoea | 30 (15) | |
| Infections and infestations | 89 (44) | |
| Upper respiratory tract infection | 31 (15) | |

Source: Ixazomib Investigator's Brochure Edition 7

Abbreviations: MedDRA = Medical Dictionary for Regulatory Activities, version 15.0.

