2. STUDY OBJECTIVES

2.1 Primary Objectives

Specific Aim 1. To determine the safety and efficacy of ixazomib as a desensitization strategy. 10 highly sensitized kidney transplant candidates on the waitlist for more than 24 months will receive ixazomib 3 mg (and dexamethasone 20 mg) on days 1, 8, and 15 of a 28 cycle for 12 months. The primary objective is to evaluate the safety (distal neuropathy, thrombocytopenia, and gastrointestinal symptoms) and efficacy (decline in cPRA > 20%) of ixazomib. The secondary efficacy endpoint is transplantation rate within 12 months of therapy.

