- Liver Function tests will be conducted twice a month (+ 6 /- 3 days) for the first 3 months, then monthly thereafter. The complete blood count (CBC) will be checked monthly. cPRA, BAFF/APRIL, DSA and antibodies will be checked every three months (5 times total). Bone marrow aspirates will be collected at the beginning and at one of the following endpoints: one month (+6, - 3 days) after the end of the 12 month study, cPRA decline > 20%, time of transplant, or time of subject withdrawal from the study. ECG and echocardiograms will be done at the baseline, 6 months, and end of the study visits.
- During the first three months of study participation, the bi-weekly Liver Function Tests may be done at the subject's local lab. The local lab will process the sample and send the result to the study team.
- Additional visits may be required if the subject has to hold treatment and needs to return to the clinic for blood draws to confirm eligibility to continue. Please see Table 4-3, Dose Adjustments for Hematologic Toxicities for dose adjustment plan.
- Data on acute rejection, graft and patient survival will be collected for six months after surgery for those subjects who receive a successful kidney transplant.

[figure not shown]
Unscheduled Visits: Subjects may have unscheduled visits due to dose adjustments based on lab results, an acute illness of undetermined cause, for other reasons, or at the discretion of the Investigator. Unscheduled visits may include any of the following procedures;

- Adverse Event Assessment
- Medication History
- Drug Accountability
- Physical Exam
- Vital Signs (Temperature, Pulse, Respirations, Blood Pressure)
- Lab work (CBC, LFTs, cPRA, BAFF/APRIL, DSA Antibodies)
- Bone Marrow Aspiration

Early Termination Visit: All subjects who end study participation prior to the end of the scheduled treatment will undergo an early termination visit within one week from study discontinuation. The early termination visit will consist of the following procedures;

- Adverse Event Assessment
- Medication History
- Drug Accountability
- Physical Exam
- Vital Signs (Temperature, Pulse, Respirations, Blood Pressure)
- Lab work (CBC, LFTs, cPRA, BAFF/APRIL, DSA Antibodies)
- Bone Marrow Aspiration (bone marrow aspiration will be done within 48 hours of transplant)

Figure 1. Study Overview Diagram

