6.2 Study Drug Administration

- Ixazomib and dexamethasone will be taken based on the information in the package insert.
- The starting dose of ixazomib will be 3 mg taken orally on days 1, 8, and 15 of a 28-day cycle. The dose of dexamethasone will be 20 mg taken orally on the same days as ixazomib.
- Patients will take ixazomib and dexamethasone for twelve (12) 28-day cycles.
- Ixazomib should be taken once a week on the same day and at approximately the same time for the first three weeks of a four week cycle. Ixazomib should be taken at least one hour before or at least two hours after food. The whole capsule should be swallowed with water. The capsule should not be crushed, chewed or opened. If an ixazomib dose is delayed or missed, the dose should be taken only if the next scheduled dose is ≥ 72 hours away. A missed dose should not be taken within 72 hours of the next scheduled dose. A double dose should not be taken to make up for the missed dose. If vomiting occurs after taking a dose, the patient should not repeat the dose. The patient should resume dosing at the time of the next scheduled dose.
- Ixazomib and dexamethasone should not be taken at the same time, because dexamethasone should be taken with food and ixazomib should not be taken with food.
- Ixazomib and dexamethasone will be dispensed monthly by the PRC
- Diaries/logs will be used by patients to track their doses.

Treatment Plan and Laboratory Assessment. Participants will undergo a 12-month treatment

regimen of ixazomib-dexamethasone on days 1, 8, and 15 of a 28-day cycle, for 12 cycles (Table 1-1 below). The dose of ixazomib (3 mg) is based on packet information for patients with reduced kidney function and will be taken at least one hour before or at least two hours after food. The dose of dexamethasone is 50% lower than the dose recommended in the package insert to reduce the possibility of metabolic complications in ESRD.

Table 1-1 IXADES Treatment Protocol for desensitization

| 28-Day Cycle (a 4-week cycle) | | | | | | | | |
|-------------------------------|--------|----------|--------|-----------|--------|------------|--------|------------|
| | Week 1 | | Week 2 | | Week 3 | | Week 4 | |
| | Day 1 | Days 2-7 | Day 8 | Days 9-14 | Day 15 | Days 16-21 | Day 22 | Days 23-28 |
| Ixazomib (NINLARO) 3 mg | ✓ | | ✓ | | ✓ | | | |
| Dexamethasone 20 mg | ✓ | | ✓ | | ✓ | | | |

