9. SAFETY MONITORING

9.1 Safety Monitoring

The investigator is responsible for monitoring the safety of subjects who have enrolled in the study. For this study, adverse events will be solicited from subjects to identify an occurrence or worsening of an unintended sign or symptom, related to the ingestion of the study drug. The study team will ask subjects prior to each cycle if they experienced any new medical related signs or symptoms since taking the study drug. Subjects will be asked about any adverse events they may have experienced again monthly, prior to each cycle, and at the five study visits. Only the adverse events considered related (possibly, probably or definitely) to the ingestion of the study drug will be entered into and managed in the ICTR OnCore system quarterly.

At each visit, subjects will be assessed for AEs by the study team. They will be examined by the principal investigator 5 times (please see tables 2-1 a-b and Figure 1, below): Days 1, 85, 169, 253, and 373 + 6, - 3).

- Day 1: Prior to treatment initiation. H&P, Labs, Bone Marrow Aspirate
- Day 85 + 6, - 3: Prior to treatment dose. H&P, Labs
- Day 169 + 6, - 3 Prior to treatment dose. H&P, Labs
- Day 253 + 6, - 3 Prior to treatment dose. H&P, Labs
- Day 373 + 6, - 3 After treatment completion, H&P, Labs, Bone Marrow Aspirate
- Study drug will be dispensed at each month's in-person visit, prior the initiation of the next cycle, and after reviewing the AEs and monthly labs.

- Patients will undergo monthly CBC and bi-weekly liver function tests (LFTs) for the first three months. After the first 3 months, CBCs and LFTs will be done monthly. cPRA, BAFF/APRIL, DSA and antibodies will be checked every three months (5 times total). Bone marrow aspirates will be collected at the beginning and at one of the following time points: one month (+ 6, - 3 days) after the end of the 12 month study, cPRA<80%, time of transplant, or time of subject withdrawal from the study.
- Additional visits may be required if the subject has to hold treatment and needs to return to the clinic for blood draws to confirm eligibility to continue. Please see Table 4-3, Dose Adjustments for Hematologic Toxicities for dose adjustment plan.

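### No scheduled blood count falls between Day 2 and Day 28 of any cycle, so thrombocytopenia that develops and recovers within a cycle may be missed

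*Combined protocol and SAP*

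**What the plan says.** Dosing (section 6.2): "The starting dose of ixazomib will be 3 mg taken orally on days 1, 8, and 15 of a 28-day cycle", for twelve cycles.

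Blood counts: section 4.1 says "The complete blood count (CBC) will be checked monthly", and sections 6.3, 7.1.8 and 9.1 agree. Section 9.1 sets the two laboratory schedules side by side: "Patients will undergo monthly CBC and bi-weekly liver function tests (LFTs) for the first three months". In Tables 2-1(a) and (b) the CBC is marked at screening, on the first day of each of the 12 cycles and at Day 373. The last columns of Table 2-1(b) are headed "309 | 316 | 323 | 373"; the CBC is marked under the first and last of these and not under the two between. Liver tests carry three extra marks, on Days 15, 43 and 64. Section 4.1 has the monthly laboratory results reviewed before the next cycle's drug is dispensed, so each cycle-start count is pre-dose.

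Outside the fixed schedule, section 4.1 allows a CBC at unscheduled visits and lists one for the early termination visit.

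Role of the result: section 2.1 states "The primary objective is to evaluate the safety (distal neuropathy, thrombocytopenia, and gastrointestinal symptoms" and efficacy. Section 3.1 lists leucopenia, anemia and thrombocytopenia in the safety endpoint. Section 7.1, however, tests discontinuation of therapy due to adverse events, and the objectives entry in the protocol summary ranks toxicity as secondary.

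**The concern.** Thrombocytopenia is one of three effects named in the primary safety objective, and section 1.10 puts it first among the areas to be watched closely. Tables 3-2 and 3-3 report it in 34% and 28% of patients, and Table 3-1 lists it as dose-limiting in C16003, C16006 and C16007. Yet every scheduled on-treatment count is taken after the dose-free part of the cycle. A count taken then records what has persisted to the next cycle, not what occurred during dosing.

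The adverse-event definition compounds this. Under section 8.1.1 an abnormal laboratory value becomes an adverse event only if it leads to action on treatment or an intervention, or if the investigator considers it clinically significant. Section 9.1 adds that the principal investigator will not make that significance judgement for laboratory results abstracted from the medical record. An unsampled, symptomless fall has little chance of entering the data, and the DMC reviews the same data.

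The plan already draws mid-cycle blood in cycles 1 to 3 for liver tests, and gives no reason for leaving the blood count off those samples.

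**Working it through.** **The plan's own figures.** The plan gives no calculation for platelet sampling. Its only computed design figures (section 7.1.1) concern efficacy, and they reproduce: the exact 95% interval for 3/10 is 6.7% to 65.2%, and 1 − 0.8^10 = 0.893, above the stated 80%.

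**Step 1: time from last dose to each scheduled count.** Inputs are the dosing days in section 6.2 and the CBC marks in Tables 2-1(a) and (b). For cycle c = 0 to 11, doses fall on Days 28c + 1, 28c + 8 and 28c + 15, and counts on Day 28c + 1, plus Day 373.

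- Day 1: before treatment.
- Days 29, 57, 85, 113, 141, 169, 197, 225, 253, 281 and 309 (11 counts): (28c + 1) − (28(c − 1) + 15) = 14 days after the previous dose.
- Day 373: 373 − 323 = 50 days after the last dose.

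With the +6/−3 day window applied to the draw and doses kept on schedule, the 14-day gap becomes 11 to 20 days. No scheduled count falls on Days 2 to 28 of any cycle.

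**Step 2: comparison with liver tests.** Days 15, 43 and 64 are each 7 days after the preceding dose (Days 8, 36 and 57). Days 15 and 43 are the third dosing day of cycles 1 and 2 (43 − 28 = 15). Day 64 is the second dosing day of cycle 3 (64 − 56 = 8), which breaks the pattern. Marked on-study draws total 13 for CBC and 13 + 3 = 16 for liver tests.

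**Step 3: direction.** One sample per cycle can miss an episode that resolves before the sample. It cannot create one.

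**Step 4: illustrative size.** The documents do not say when platelets reach their lowest point or how fast they recover, so episode length D is an assumption. If onset is uniform over the 28 days, one draw per cycle sees an episode with probability min(1, D/28). The background rates are 49/173 = 28% (Table 3-3) and 68/201 = 34% (Table 3-2). With 10 patients and one episode per affected patient, 2.8 to 3.4 patients would be affected:

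| Assumed D (days) | Chance seen | Expected count seen at 28% | Expected count seen at 34% |
|---|---|---|---|
| 7 | 25% | 0.70 | 0.85 |
| 10 | 36% | 1.00 | 1.21 |
| 14 | 50% | 1.40 | 1.70 |
| 21 | 75% | 2.10 | 2.55 |
| 28 or more | 100% | 2.80 | 3.40 |

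The result is sensitive to both assumptions. If onset is confined to cycle Days 8 to 22, a 7-day episode is never seen at the next cycle start, while a 21-day episode is seen in 14/15 = 93% of cases. If a patient has three independent 7-day episodes with uniform onset, the chance that at least one is seen is 1 − 0.75^3 = 58%.

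**The case against.** The strongest reply is that monthly counts are a coherent choice. They are stated the same way throughout, they match the decision they serve (whether the next cycle may begin, section 6.3.1), and this is a 10-patient pilot. Much of that stands: there is no contradiction in the CBC schedule itself. But a check made before dispensing is not a measure of incidence, and sections 2.1 and 3.1 name thrombocytopenia as a result of the trial.

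Several stronger readings are tempting but not supported:

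- **That thrombocytopenia is likely undercounted.** Section 1.4 reports a "2fold accumulation (based on AUC) following the Day 15 dose" and a 9.5-day half-life, and a reader might infer that platelets are lowest then and recovered by Day 29. These are plasma figures. The documents say nothing about platelet timing, and if low counts persist to the next cycle nothing is lost.
- **That such falls can never be seen, or that incidence cannot be reported.** Unscheduled and early-termination counts exist. They follow dose adjustments, illness, investigator discretion or withdrawal, so they would not reliably find a silent fall, but the absolute claim fails.
- **That platelets are sampled half as often as liver function.** This describes cycles 1 to 3 only. Over the study the marks are 13 against 16, and frequency is equal after month 3.
- **That the 34% and 28% forecast this trial.** They are pooled from oncology studies with various doses, and both pools include twice-weekly dosing. Thrombocytopenia was not among the dose-limiting toxicities of C16004, the weekly single-agent myeloma study.

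It is also fair to object that adding counts on Days 15, 43 and 64 does not cover the days after the third dose. That is correct and limits the fix.

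**Conclusion.** The point holds as a limitation of measurement. All 11 on-treatment counts are pre-dose and nominally 14 days after the previous dose, and the Day 323 dose has no scheduled count for 50 days. Thrombocytopenia that comes and goes within a cycle may therefore be missed, apart from unscheduled or early-termination counts, and the bias can only run toward appearing safer.

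Its size cannot be fixed from the documents. Under uniform onset and one episode per affected patient, the loss is nil for assumed episodes of 28 days or more and about three quarters for 7-day episodes. At the 34% background rate that means between 3.4 and 0.85 of 10 patients seen.

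The effect is on the descriptive hematologic results promised in sections 2.1 and 3.1. The safety endpoint that section 7.1 tests, discontinuation due to adverse events, is affected only indirectly. A reader might infer that the formal safety test is compromised; the documents do not support that. The sections that rank safety as primary or secondary, and that define its endpoint differently, should be reconciled so that it is clear which result this limitation touches.

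**What to change.** 1. In Table 2-1(a), add a CBC to the mid-cycle blood already drawn for liver tests in cycles 1 to 3, marked on Days 15, 43 and 64, with the local-laboratory allowance that section 4.1 gives the liver tests. Confirm the Day 64 mark first, since the other two fall on the third dosing day of their cycle.
2. In section 7.1.8, report thrombocytopenia, leucopenia and anemia as the worst value at any draw, with the cycle-start values shown alongside.
3. This is a partial remedy: nominally, the days after the third dose and all of cycles 4 to 12 stay unsampled. Label hematologic results from cycles without a mid-cycle count as taken at cycle start, and state that transient falls may be missed. The labelling costs nothing and is justified whatever the platelet time course.

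Cost: 3 draws × 10 patients = about 30 extra CBCs on blood already scheduled, with no new visit or needle stick. The downside is a small laboratory cost and more transient low counts to report. Section 6.3.1 and Table 4-2 are framed around starting a cycle, so the sponsor should check how they apply to a mid-cycle value. No dose or hold rule is proposed here.
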